## **The American British Cowdray Medical Center**

**Date: March 26, 2020**

**NCT05807945**

### **Comparison of Intra-articular 0.2% Ropivacaine vs 0.75% Ropivacaine in Postoperative Knee Arthroscopy**

#### **Abstract:**

All patients with acute lesions assistant to the orthopedic and trauma center of the ABC medical center will be invited to participate in the study. Those that meet the inclusion criteria and later sign an informed consent will be randomized to receive 10 ml of a solution with ropivacaine at 0.75% and 0.2% intraarticular for the first 5 minutes after the end of surgery (closing of surgical wounds). Both the patient, the physician who applies it and the evaluator of outcomes remain blinded to the dose of ropivacaine the patient receives.

Two hours after the end of the surgery, while the patient is in his room, the presence of pain will be evaluated by a visual analog scale (EVA), while the patient is asked to flex and extend his knee. The result will be quantified continuously, to later categorize the pain in none to slight pain (0-3 points) and moderate-severe pain (4-10 points). All the information will be recorded on established forms in the clinical file (general data), that includes the variables of interest for the study, and is reported by the physicians after standardization of all those encharged with collecting information to comply with the conceptual and operative

operationalization of the variables described in the research protocol. In addition to the evaluation of pain, the administration of opiodes to patients for necessary reasons (presence of pain) by the physicians in charge is recorded.

It is hoped that, in patients with knee arthroscopy for acute lesion, there is a difference in the frequency of moderate-severe pain of 30% in the post-operative (frequency of 37.5% in patients with ropivacaine at 2% and frequency of 7.5% in patients with ropivacaine at 7.5%).

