## **Objectives**

General objective:

- To evaluate the analgesic effect of the intra-articular administration of 0.75% ropivacaine in the immediate postoperative period of knee arthroscopy in acute injuries.

Specific objectives:

- To evaluate the effect of intra-articular administration of 0.75% ropivacaine in reducing opioid consumption in the immediate postoperative period of knee arthroscopy in acute injuries.
- To evaluate the effect of intra-articular administration of 7.5% ropivacaine on mobility in the immediate postoperative period of knee arthroscopy in acute injuries.

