### *Exit from the study:*

- Any transoperative event that requires the suspension of surgery.
- Any transoperative event that impedes the application of intraarticular ropivacaine.

The patients in both arms receive 10 ml of intraarticular solution in the knee (at the anatomical point at the level of the upper pole of the ball joint, under the iliotibial band), with different content of ropivacaine; the vehicle for application presents the same physical appearance for all patients and is applied by previously standardized treating physicians.

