### *Sample size*

Expecting an absolute difference, an absolute difference of 30% is expected for the presence of moderate-severe pain, considering a level of significance=5% and power=80%. Needed are 68 subjects, 34 for each arm.

Given that the evaluation of outcome is performed 2 hrs. after the application of the maneuver, and due to the low incidence of postoperative anesthetic complications, loss of information is estimated at <1%.

*Sample size and statistical analysis:* Sample size was estimated to establish a difference of 30% in considering the presence of moderate-severe pain among patients treated with different doses of ropivacaine, considering an alpha level of 0.05 and beta of 0.20. Required

were 68 patients divided into two groups of 34 each. Loss of information was expected at <1%, and 2 subjects were added to the sample size, increasing the requirement to 70 subjects in total. For statistical analysis, the statistical program SPSS version 27 will be used (IBM Armonk, New York). Contrast of the incidence of outcomes between the two groups by different doses of ropivacaine will be carried out by  $\chi^2$  or Fisher exact test, when necessary. Multivariate analyses will be performed by logistic regression analysis, considering a value of  $p < 0.05$  as significant, and double gradient differences in exposure to different variables between treatment groups were included in multivariate analysis.

In the *intention-to-treat analysis* (ITT), the main and secondary outcomes will be contrasted between the groups, considering the randomization of the different doses of ropivacaine, and in the *per-protocol analysis (PP)*, the results of the incidence of moderate-severe pain will be contrasted between groups formed by randomization; however, those that received opioids in the first 2 hours post-surgery will be excluded, in order to know the effect of the use of ropivacaine at 7.5% without the effect of a conjugate maneuver.

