#### *Variables to be evaluated*

Dependent variable	
Pain (Primary outcome)	Conceptual definition: Sensory and emotional experience associated with a present or potential injury or a described one.  Operational definition: The sensation of painful discomfort at the surgical site (Mild, moderate or severe).  Type of variable: Dichotomous qualitative.  Measuring instrument: VAS (0-10 points)  Measurement units: Mild 0-3 points, moderate-severe 4-10 points.

Opioid use	
Conceptual definition: Drug whose analgesic action is produced thanks to the interaction with the opioid receptors of the neurons of the central nervous system.
 
Operational definition: According to the VAS pain score administration of Tradol dose of 50mg IV.
 
Type of variable: Qualitative dichotomous
 
Measuring instrument: Information extracted from the patient's file.
 
Measurement units: Not use / Use.

Mobility	
Conceptual definition: Amplitude of joint oscillation within natural limits.
 
Operational definition: The active mobility performed by the patient in the postoperative period.
 
Variable type: Dichotomous qualitative.
 
Measuring instrument: Observation made by the doctor in the postoperative period after the indication of flexion and extension of the leg, elevation and descent of it actively before the doctor.
 
Measurement units: Present / absent.

Independent variable	
Ropivacaine 0.75%	
Conceptual definition: Long-lasting amide-type local anesthetic with lower lipid solubility.
 
Operational definition: IA administration to the knee of 10 ml of 0.75% ropivacaine.
 
Variable type: Dichotomous qualitative.
 
Measuring instrument: Experimental maneuver.

	Measurement units: No / Yes
Ropivacaine 0.2%	
Conceptual definition: Long-acting amide-type local anesthetic with lower lipid solubility
 
Operational definition: IA administration to the knee of 10 ml of 0.2% ropivacaine.
 
Variable type: Dichotomous qualitative.
 
Measuring instrument: Experimental maneuver.
 
Measurement units: No / Yes

Peripheral variables/covariates/Probable confounders /Probable interactors	

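### The per-protocol analysis drops patients given an opioid in the first 2 hours, which selects on a consequence of pain and removes likely failures, more of them from the arm with more pain

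*Combined protocol and SAP*

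**What the plan says.** The section on sample size and statistical analysis plans two analyses. ITT compares the main and secondary outcomes by randomised dose. For PP it says that "the results of the incidence of moderate-severe pain will be contrasted between groups formed by randomization", but then that "those that received opioids in the first 2 hours post-surgery will be excluded". The reason given is "in order to know the effect of the use of ropivacaine at 7.5% without the effect of a conjugate maneuver". (That concentration label does not match the one in the title; the labels must be reconciled, but nothing here depends on it.)

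Other sections say what early opioid use represents:

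- Abstract: "the administration of opiodes to patients for necessary reasons (presence of pain) by the physicians in charge is recorded".
- Variables to be evaluated: opioid use is listed among the dependent variables and defined as "According to the VAS pain score administration of Tradol dose of 50mg IV". The VAS is also the instrument for the primary outcome, where 4 to 10 points is moderate-severe pain.
- Objectives: one specific objective is the effect of the 0.75% solution "in reducing opioid consumption in the immediate postoperative period".
- Model description: pain is read two hours after surgery ends, which is when the exclusion window closes.
- Exit from the study: the two reasons listed are suspension of surgery and "Any transoperative event that impedes the application of intraarticular ropivacaine". Opioid use is not among them.

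Neither ITT nor PP is named as the primary analysis.

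**The concern.** A PP set normally removes patients who did not receive the assigned treatment or were not assessed as planned. An opioid given because the patient hurts is neither. It is a response to the outcome under study, and the plan expects the dose to alter it.

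Dropping these patients does not show what their pain would have been without the opioid. It gives the pain rate among patients who were not rescued, and under the trial's own hypothesis these are a different subset in each arm. Two errors can follow:

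- If painful patients are rescued at the same rate in both arms, PP understates the difference.
- If rescue practice differs between arms, PP can show a difference that the dose did not cause.

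The plan presents PP as the analysis that isolates ropivacaine and gives no order of precedence. A PP result that conflicts with ITT could therefore be reported as the main finding.

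**Working it through.** **Inputs from the documents.** Expected moderate-severe pain is 37.5% in the lower-concentration arm and 7.5% in the higher (Abstract). There are 34 patients per arm, alpha is 0.05 (two-sided assumed), power is 80%, and the test is chi-square or Fisher exact when necessary (sample size section).

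**Step 1: the plan's own figure.** Full enumeration of the two-sided Fisher exact test at 37.5% vs 7.5% gives power 79.4% with 33 per arm and 81.0% with 34. The stated 34 per arm reproduces. The steps below read the planned test as Pearson chi-square without correction when all expected counts are at least 5, and Fisher otherwise. Without exclusions, that test has power 88.0% with 34 per arm, and a type I error of 5.5% when both arms are at 37.5%.

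**Step 2: the exclusion rule.** Let p be the true rate of moderate-severe pain and f the share of painful patients given an opioid before 2 hours. Assume no pain-free patient receives one. Then:

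- patients removed per arm = 34·p·f
- PP rate = p(1 − f)/(1 − pf)

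The ratio of exclusions is 0.375/0.075 = 5 to 1 for any common f. For f = 0.50:

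- 0.2% arm: 34 × 0.375 × 0.50 = 6.4 removed; rate 0.1875/0.8125 = 23.1%.
- 0.75% arm: 34 × 0.075 × 0.50 = 1.3 removed; rate 0.0375/0.9625 = 3.9%.

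**Step 3: same share excluded in both arms (Assumption A).** Power is by exact enumeration with the PP group sizes rounded.

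| f | PP n | PP rates | Difference (points) | Power |
|---|---|---|---|---|
| 0 | 34 + 34 | 37.5% vs 7.5% | 30 | 88% |
| 10% | 33 + 34 | 35.1% vs 6.8% | 28 | 86% |
| 25% | 31 + 33 | 31.0% vs 5.7% | 25 | 77% |
| 50% | 28 + 33 | 23.1% vs 3.9% | 19 | 59% |
| 75% | 24 + 32 | 13.0% vs 2.0% | 11 | 23% |

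If the PP group sizes vary at random instead of being fixed, power in the last four rows is 85%, 77%, 57% and 25%.

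**Step 4: some pain-free patients also receive an opioid.** With a share g of them, the PP rate is p(1 − f)/[1 − pf − (1 − p)g]. For f = 0.50, g = 0.05 and 35 per arm, 7.7 vs 2.9 patients are removed, the rates are 24.0% vs 4.1%, and the difference is 19.9 points. The selection disappears only if f = g, that is, if early opioid use is unrelated to pain.

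**Step 5: no true difference, unequal rescue (Assumption B).** Both arms have 37.5% pain, but the share of painful patients rescued differs.

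| Rescue shares | PP n | Probability of a significant PP result |
|---|---|---|
| 40% vs 40% | 29 + 29 | 4.7% |
| 50% vs 40% | 28 + 29 | 5.4% |
| 50% vs 30% | 28 + 30 | 8.1% |
| 60% vs 20% | 26 + 31 | 19% |

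With random group sizes these are 4.9%, 5.7%, 8.3% and 19.4%.

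**Step 6: rescue that works before the 2-hour reading.** Let p now be the pain rate before any opioid, and let a share m of rescued patients fall to VAS 0-3 by 2 hours. The ITT rate becomes p(1 − fm); the PP rate is unchanged.

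| f | m | ITT difference (points) | PP difference (points) |
|---|---|---|---|
| 25% | 50% | 26.3 | 25.3 |
| 25% | 100% | 22.5 | 25.3 |
| 50% | 50% | 22.5 | 19.2 |
| 50% | 100% | 15.0 | 19.2 |

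**The case against.** The strongest reply is that early rescue also affects ITT. Step 6 shows that if every rescued patient responds, PP lies closer to 30 points than ITT does. At f = 50%, ITT has power 36% against 59% for PP. This stands as a limit on the sizes in Step 3, which take the opioid as not bringing the VAS below 4 by 2 hours. It also means an excluded patient is a likely failure, not a certain one. It does not justify the rule: PP is still below 30 points in every case and still selects on a consequence of pain. ITT remains a valid comparison of pain under usual rescue.

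Other points are fair in part:

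- **Only PP is affected.** True. ITT is planned and covers every outcome, so this is a flaw to correct and not a threat to the trial.
- **The early opioid rate may be small.** The only scheduled VAS is at 2 hours, so few opioids may precede it. At a 10% share the effect is minor.
- **The bias runs against the 0.75% arm.** This holds when rescue shares are equal. The patient, the injecting physician and the assessor are blinded, and nothing in the documents suggests unequal rescue. Modest imbalance (50% vs 40%) gives 5.4%, against 5.5% for the same test without exclusion, and 60% vs 20% is extreme.
- **The exit criteria are not a list of PP deviations, and the PP sentence discloses its restriction.** Both are true, so neither proves the point alone. The argument rests on the opioid being triggered by pain and being an outcome.
- **PP was never powered separately.** True. The planned 80% is only a yardstick here.

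**Conclusion.** The concern holds. By the plan's own definitions, the PP rule conditions on a post-randomisation event that is driven by pain and expected to differ by dose. That conclusion needs no assumption about rates beyond early opioid use being related to pain, which the Abstract and the variable definitions both state.

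The size is illustrative, because the documents give no early opioid rate. Under equal rescue shares the distortion is minor at 10%, and PP power falls below 80% from about 25%. False-positive results become a material risk only if rescue differs widely between arms. The absence of a stated primary analysis would be a small gap on its own, but it makes this flaw more consequential. The plan should be corrected, and confidence in the finding is high.

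**What to change.** 1. Remove the opioid exclusion from PP. Define PP by true deviations: infiltration not given (consistent with the exit criteria), wrong concentration given, or pain not assessed at the planned time.
2. State that ITT is the primary analysis and PP is supportive.
3. Keep the 2-hour VAS, regardless of opioid use, as the primary outcome, and report opioid use by arm beside it.
4. Pre-specify one ITT sensitivity analysis in which failure is VAS 4-10 at 2 hours or an opioid given for pain before that reading. Otherwise a rescued patient who reads 0-3 counts as having no more than slight pain.

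The cost is a few sentences in the analysis section, with no change to sample size, primary outcome or patient care. The time of opioid administration must be recorded, since the variable is now only use or non-use, but the current PP rule needs that too. The drawback is that the composite in item 4 mixes the clinician's decision to rescue with the patient's score and overlaps the opioid outcome, so it should remain a sensitivity analysis.

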#### *Variables to be evaluated*

Dependent variable	
Pain (Primary outcome)	Conceptual definition: Sensory and emotional experience associated with a present or potential injury or a described one.  Operational definition: The sensation of painful discomfort at the surgical site (Mild, moderate or severe).  Type of variable: Dichotomous qualitative.  Measuring instrument: VAS (0-10 points)  Measurement units: Mild 0-3 points, moderate-severe 4-10 points.

Opioid use	
Conceptual definition: Drug whose analgesic action is produced thanks to the interaction with the opioid receptors of the neurons of the central nervous system.
 
Operational definition: According to the VAS pain score administration of Tradol dose of 50mg IV.
 
Type of variable: Qualitative dichotomous
 
Measuring instrument: Information extracted from the patient's file.
 
Measurement units: Not use / Use.

Mobility	
Conceptual definition: Amplitude of joint oscillation within natural limits.
 
Operational definition: The active mobility performed by the patient in the postoperative period.
 
Variable type: Dichotomous qualitative.
 
Measuring instrument: Observation made by the doctor in the postoperative period after the indication of flexion and extension of the leg, elevation and descent of it actively before the doctor.
 
Measurement units: Present / absent.

Independent variable	
Ropivacaine 0.75%	
Conceptual definition: Long-lasting amide-type local anesthetic with lower lipid solubility.
 
Operational definition: IA administration to the knee of 10 ml of 0.75% ropivacaine.
 
Variable type: Dichotomous qualitative.
 
Measuring instrument: Experimental maneuver.

	Measurement units: No / Yes
Ropivacaine 0.2%	
Conceptual definition: Long-acting amide-type local anesthetic with lower lipid solubility
 
Operational definition: IA administration to the knee of 10 ml of 0.2% ropivacaine.
 
Variable type: Dichotomous qualitative.
 
Measuring instrument: Experimental maneuver.
 
Measurement units: No / Yes

Peripheral variables/covariates/Probable confounders /Probable interactors	
Sex	
Conceptual definition: Organic condition of the individual.
 
Operational definition: Identification of the individual as Male or Female.
 
Type of variable: Dichotomous qualitative.
 
Measurement units: Male / Female.

Age	
Conceptual definition: Time lived by a person.
 
Operational definition: 18-35 years; 36 – 60 years.
 
Variable type: qualitative ordinal
 
Measurement units: 18-35; 36-60

BMI	
Conceptual definition: Mathematical reason that associates weight and height.
 
Operational definition: 1. normal weight BMI<25 vs 2. overweight BMI≥25

	
Variable type: qualitative ordinal
 
Measurement units: kg/m^2

Time of evolution	
Conceptual definition: Duration from the onset of symptoms or their detection
 
Operational definition: 1. <4 weeks and 2. >5 weeks
 
Variable type: qualitative ordinal
 
Measurement units: number of weeks

Physical activity	
Conceptual definition: Any body movement produced by skeletal muscles that requires energy expenditure
 
Operational definition: active vs sedentary
 
Variable type: dichotomous qualitative
 
Measurement units: 0-1

Etiology of surgery	
Conceptual definition: Cause of the organism before the disease
 
Operational definition: traumatic vs degenerative
 
Variable type: dichotomous qualitative
 
Measurement units: 0-1

Duration of Surgery	
Conceptual definition: Time spent performing interventions inside and outside the human body
 
Operational definition: 1. <45 min and 2. <math>\geq</math> 45 min
 
Variable type: qualitative ordinal
 
Measurement units: minutes

Type of articular cartilage injury	
Conceptual definition: Description of the different degrees of chondropathy
 
Operational definition: I: 0mm, II: < 0.5mm and III : >0.5mm
 
Variable type: qualitative ordinal
 
Measurement units: millimeters

---	--

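### The opioid outcome records only whether a patient received an opioid, so it cannot show whether the amount consumed fell, and its drug scope and time window need reconciling

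*Combined protocol and SAP*

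**What the plan says.** All references are to the combined protocol and SAP.

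- **Objectives, specific objectives.** The aim is "To evaluate the effect of intra-articular administration of 0.75% ropivacaine in reducing opioid consumption in the immediate postoperative period". The Justification gives lower opioid consumption as a reason for the trial. The Background uses the same term as a quantity, citing a median of 11.3 (0-52) pills.
- **Variables to be evaluated, Opioid use.** The conceptual definition is class-wide: "Drug whose analgesic action is produced thanks to the interaction with the opioid receptors of the neurons of the central nervous system". The operational definition is "According to the VAS pain score administration of Tradol dose of 50mg IV". The type is "Qualitative dichotomous", the values are Not use / Use, and the source is "Information extracted from the patient's file".
- **Abstract.** Opioids are mentioned without naming a drug: "the administration of opiodes to patients for necessary reasons (presence of pain) by the physicians in charge is recorded".
- **Sample size and statistical analysis.** Incidences are compared between arms by chi-square or Fisher's exact test. In the per-protocol analysis, "those that received opioids in the first 2 hours post-surgery will be excluded"; again no drug is named.

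No variable records total dose, number of doses or time of administration. No analysis of amount is planned.

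**The concern.** Consumption is an amount, and the variable is a yes/no. Two patients given different total doses are both recorded as Use, so a change in dose among users is invisible. If the use rates were similar, the trial could report no effect on opioid consumption when the amount had in fact changed. If the use rates differed, a statement about consumption would still go further than the data.

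The variable is also not defined tightly enough for two people abstracting the same file to be sure of agreeing. The operational definition names one product, one dose and one route, while three other places refer to opioids as a class. No rule says how another opioid is to be coded, and no passage says that Tradol is the only one given. The objective's period is the immediate postoperative one, without a cut-off. The 2-hour limit is attached only to the per-protocol exclusion.

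Finally, if administration follows the VAS, opioid use overlaps with the primary outcome, which is itself a cut of the VAS.

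**Working it through.** **1. The plan's own figure.** The documents give no rate, effect size or power for the opioid outcome. The only sample size is 34 per arm (68, raised to 70) for pain at 37.5% versus 7.5%, with alpha 0.05 (taken as two-sided) and beta 0.20. Exact enumeration of Fisher's test gives power of 79.4% at 33 per arm and 81.0% at 34, so 34 is reproduced. It was derived for pain and says nothing about opioid use.

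**2. What the binary variable misses.** Assumptions not in the documents: the same share u of each arm uses an opioid, and users average 150 mg in one arm and 50 mg in the other. Mean dose per patient = u × mean dose per user.

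- u = 0.40: 0.40 × 150 = 60 mg and 0.40 × 50 = 20 mg. Difference in amount: 40 mg. Difference in use: 0.40 − 0.40 = 0.
- u = 0.30: 45 mg and 15 mg. Difference in amount: 30 mg. Difference in use: 0.

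**3. What the unsettled drug scope could do.** One patient coded differently moves an arm's use rate by 1/34 = 2.9 points. For a range, borrow the pain rates as true any-opioid use (37.5% versus 7.5%, an assumption). Let a share s of users receive only another opioid and be coded Not use. Observed rates are 0.375(1 − s) and 0.075(1 − s). With n = 35 per arm and p̄ the mean of the two observed rates p₁ and p₂,

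power = Φ{[(p₁ − p₂) − 1.96·√(2p̄(1 − p̄)/n)] / √([p₁(1 − p₁) + p₂(1 − p₂)]/n)}.

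| s | Observed difference (points) | Power |
|---|---|---|
| 0 | 30 | 87% |
| 10% | 27 | 82% |
| 20% | 24 | 75% |
| 30% | 21 | 68% |
| 50% | 15 | 51% |

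The documents do not give s, and it may be zero.

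**4. Which summary of amount to use.** A rank test with a Hodges-Lehmann difference is a natural first thought, but it fails when many patients take nothing. The estimate is the median of all between-arm pairwise differences. In the step 2 example at u = 0.30, 0.70 × 0.30 = 21% of pairs are negative, 0.70 × 0.70 = 49% are zero and 30% are positive, so the median is zero. At u = 0.40 the shares are 24%, 36% and 40%, and the median is again zero. With unequal use of 37.5% versus 7.5%, 0.625 × 0.925 = 57.8% of pairs are zero, so the median is zero despite a 30-point difference in use.

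Simulation of the step 2 example at 35 per arm:

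| u | Hodges-Lehmann estimate is zero | Rank-test power | Power comparing means |
|---|---|---|---|
| 30% | about 99% of trials | about 12% | about 68% |
| 40% | about 88% of trials | about 26% | about 87% |

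A mean difference with non-users counted as zero therefore matches the objective better.

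**The case against.** The strongest reply is that the share of patients who need an opioid is a legitimate outcome and a limited form of reduced consumption. It is coherent with a plan in which pain and mobility are also dichotomous and everything is compared as an incidence. That stands: the gap is about amount, and the variable is not useless.

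Several stronger readings are tempting, and the documents do not support them.

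- *Any other opioid counts as Not use.* A reader might infer this from the operational definition, but no such rule is written. The conceptual definition, the Abstract and the per-protocol rule point the other way. The coding is ambiguous, not fixed.
- *Only one dose counts.* The text gives a dose of 50 mg and does not state a number of doses.
- *Longer stays create more users in one arm.* No length of stay is given, and nothing suggests that it would differ between randomised, blinded arms.
- *The Abstract and the variable table conflict over what triggers administration.* They can be read as compatible, since the physicians in charge may act on the VAS. Because no threshold is given, the overlap with the primary outcome is conditional and cannot be quantified.

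The reply can also point to context for the window: the objective is limited to the immediate postoperative period, and the outcome is assessed at 2 hours. This narrows the window but does not give the opioid variable a cut-off. It is also fair that the 150 versus 50 mg case is an illustration and requires equal use in both arms.

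**Conclusion.** The point holds in this form: followed exactly, the plan can show whether fewer patients received an opioid but cannot show a change in the amount consumed, which is how the objective is worded. Separately, the single-product operational definition, the class-wide references elsewhere and the missing cut-off must be reconciled before files are abstracted.

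The size is unknown, because the documents give no opioid use rates, doses per user or frequency of other opioids. Under the stated assumptions, a 40 mg per-patient difference in mean dose could register as zero. If some users' opioids were not counted, a true 30-point difference in use could appear as 27 to 15 points. Neither is a forecast.

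This concerns a named specific objective and part of the trial's rationale. It does not touch the primary outcome or the sample size. It is worth correcting because the correction is cheap, and without it a conclusion about consumption would exceed the data.

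**What to change.** 1. **Keep Use / Not use and define it fully.** Count any systemic opioid within one fixed post-surgery window common to both arms. Align the operational definition, conceptual definition, Abstract and per-protocol rule with it.
2. **Abstract drug, dose and clock time** from the patient's file, which is already the named source. Clock time also makes the 2-hour per-protocol exclusion reproducible.
3. **Compare total dose per patient** as a mean difference, with non-users as zero and a bootstrap or permutation interval. Use opioid equivalents with a conversion stated in advance, or mg if only Tradol is given. Do not rely on a Hodges-Lehmann difference.
4. **If dose is not abstracted,** reword the objective as the proportion of patients receiving an opioid.
5. **In either case,** state in the report that opioid use triggered by the VAS is not independent confirmation of the primary result.

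The cost is one reworded variable, three items per administration from a file already being read, and one further analysis. Patient care does not change.
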